10.3.6.1. Subgroup Analyses.....	58
10.3.6.2. Interim Analyses.....	58
11. References	59
12. Appendices	61

List of Tables

Table		Page
Table GPGF.1.	Schedule of Activities	12
Table GPGF.2.	Objectives and Endpoints.....	18
Table GPGF.3.	Study Treatments and Dose Titration.....	32
Table GPGF.4.	Dose–Response Assumption Used in Sample Size Determination.....	52
Table GPGF.5.	Definitions of Populations to Be Analyzed in Study GPGF	52

List of Figures

Figure

Page

Figure GPGF.1. Illustration of study design for clinical protocol I8F-MC-GPGF..... 19

List of Appendices

Appendix		Page
Appendix 1.	Abbreviations and Definitions.....	62
Appendix 2.	Clinical Laboratory Tests.....	66
Appendix 3.	Study Governance Considerations.....	68
Appendix 4.	Hepatic Monitoring Tests for Treatment-Emergent Abnormality.....	72
Appendix 5.	Criteria for Diagnosing Type 2 Diabetes Mellitus (American Diabetes Association 2017).....	73
Appendix 6.	Contraceptive Methods.....	74
Appendix 7.	World Health Organization Standardized Protocols for the Measurement of Height and Weight.....	76

1. Synopsis

Title of Study:

A Phase 2, Double-Blind, Placebo-Controlled, 3-Month Trial of LY3298176 versus Placebo in Patients with Type 2 Diabetes Mellitus

Rationale:

Study I8F-MC-GPGF is a 3-month Phase 2 study designed to examine the efficacy and tolerability of subcutaneously administered once-weekly (QW) LY3298176 compared with placebo in patients with type 2 diabetes mellitus (T2DM) who have inadequate glycemic control with diet and exercise alone or with a stable dose of metformin. This study will use 3 different titration schemes of LY3298176 to reach the highest planned dose. The primary endpoint will be the change from baseline in hemoglobin A1c (HbA1c) at the end of study drug treatment. Efficacy and tolerability data from this study and from the large Phase 2 study I8F-MC-GPGB (GPGB) will be used to set doses and titration scheme for the Phase 3 studies.

Objectives/Endpoints:

Objectives	Endpoints

Primary
 
 To demonstrate that at least 1 LY3298176 titration scheme is superior to placebo in hemoglobin A1c (HbA1c) reduction at 3 months in patients with type 2 diabetes mellitus (T2DM) inadequately controlled with diet and exercise alone or treated with a stable dose of metformin 	
 Change in HbA1c from baseline

Secondary
 
Efficacy
 
 To compare each titration scheme to placebo at 3 months for secondary efficacy parameters 
Safety
 
 To compare each titration scheme to placebo for selected safety parameters at 3 months 
Pharmacokinetics
 
 To evaluate the pharmacokinetics (PK) of LY3298176 	
 Proportion of patients achieving HbA1c target of <7.0% The change in fasting blood glucose (FBG; central laboratory) from baseline The change in body weight from baseline The change in waist circumference from baseline Treatment-emergent adverse events (TEAEs) and serious adverse events (SAEs) Incidence of nausea, vomiting, and diarrhea Discontinuation of study drug due to adverse events (AEs) Incidence and rate of hypoglycemia (severe, total, documented symptomatic, and nocturnal) Incidence of anti-LY3298176 antibodies PK trough samples

Summary of Study Design:

LY3298176 is being investigated for its potential use in the treatment of T2DM. LY3298176 is a long-acting, dual incretin receptor co-agonist that binds to both the glucose-dependent insulinotropic polypeptide (GIP) receptor and the glucagon-like peptide-1 (GLP-1) receptor. Study GPGF is a Phase 2, multicenter, randomized, double-blind, parallel-arm, placebo-controlled titration study designed to evaluate efficacy, tolerability, and safety of LY3298176 in patients with T2DM with inadequate glycemic control on diet and exercise alone or on a stable dose of metformin monotherapy.

Treatment Arms and Duration:

Study GBGF includes 4 treatment arms: 3 titration arms of LY3298176 and matching placebo. Patients will be randomized in a 1:1:1:1 ratio to 1 of the 3 LY3298176 titration groups or placebo. Study participants will be treated for 3 months after randomization in a double-blind manner, followed by a 4-week safety evaluation.

Number of Patients:

A total of approximately 92 patients (23 patients per titration group or placebo) will be randomized, and approximately 80 are expected to complete the treatment period.

Statistical Analysis:

Efficacy: The primary analysis for the endpoint of the primary objective, change from baseline in HbA1c at 3 months, will be mixed model for repeated measures (MMRM) analysis. It will be performed on the modified intent-to-treat (mITT) analysis data set. This model will include baseline body mass index (BMI; <30 , ≥ 30), metformin use, treatment, visit, and treatment-by-visit as fixed effects, and baseline HbA1c value as a covariate.

Additional covariates may be added and will be detailed in the statistical analysis plan (SAP).

The mean weight change from baseline at 3 months will be analyzed using similar MMRM models as the primary analysis with treatment, visit, treatment-by-visit, metformin use, baseline HbA1C category ($<8.5\%$, $\geq 8.5\%$) as fixed effects, and baseline body weight as covariate. The change from baseline of fasting blood glucose (FBG) and waist circumference will be analyzed using a similar MMRM-based model. Summaries will include descriptive statistics for continuous measures (sample size, mean, standard deviation [SD], median, minimum, and maximum) and for categorical measures (sample size, frequency, and percentage).

Safety: The summary statistics for continuous variables will be sample size, mean, SD, median, minimum, and maximum. The summary statistics for categorical variables will be sample size, frequency, and percentage. Exposure to each therapy during the treatment period of the study will be calculated for each patient and summarized by treatment group. Additional analyses, such as concentration–safety lab plots, may be performed if warranted upon review of the data.

Pharmacokinetics (PK)/Pharmacodynamics (PD): Trough PK samples collected over the course of this study will be used to assess that LY3298176 exposures in the study are consistent with known LY3298176 PK. Additionally, PK/PD data from this study may be used as a validation dataset to enable evaluation of PK/PD models developed from the core Phase 2 study GPGF

data. These analyses may be conducted using nonlinear mixed-effects modeling implemented with the NONMEM software. If positive antibody titers to LY3298176 are observed, the relationship between antibody titer and LY3298176 PK or any relevant PD parameters will be evaluated.

2. Schedule of Activities

Table GPGF.1. Schedule of Activities

Study Phase	Screen	Lead-In	Randomize	Treatment							Follow-Up	Early Term.
				4	5	6	7T ^a	8	9T ^a	10 ^b		
Visit	1	2	3	4	5	6	7T ^a	8	9T ^a	10 ^b	801 ^d	ET
Week of Treatment	-2	-1	0	1	2	4	4	8	8	12	(15)	
Study Day/(dose number)			0/(1)	7/(2)	14/(3)	28/(5)	31-34	56/(9)	59-62	84	105	
Visit Window (days)		+7	0	0	±2	±3		±3		±3	±3	
Administrative												
Informed consent	X											
Diabetes medical history/therapy	X											
Inclusion/exclusion	X	X	X									
Preexisting conditions	X											
Randomization			X									
IWRS	X	X	X	X	X	X		X		X	X	X
BG meter/supplies, if needed		X										
BG meter, instructions		X										
Diet, exercise, BG counseling		X										
Study diary, dispense		X	X	X	X	X		X		X		
Review patient diaries for BG values, AEs, hypoglycemic or hyperglycemic events		X	X	X	X	X		X		X	X	X
Subcutaneous injection training		X	X	X	X	X		X				
Study drug and injection supplies, dispense			X	X	X	X		X				
Health habits (alcohol use, tobacco use current/past)	X											
Patient returns study drug vials						X		X		X		
Study drug, assess compliance			X	X	X	X		X		X		
Patient Demographics												
Age	X											
Gender	X											
Race/ethnicity	X											

Study Phase	Screen	Lead-In	Randomize	Treatment							Follow-Up	Early Term.
				4	5	6	7T ^a	8	9T ^a	10 ^b		
Visit	1	2	3	4	5	6	7T ^a	8	9T ^a	10 ^b	801 ^d	ET
Week of Treatment	-2	-1	0	1	2	4	4	8	8	12	(15)	
Study Day/(dose number)			0/(1)	7/(2)	14/(3)	28/(5)	31-34	56/(9)	59-62	84	105	
Visit Window (days)		+7	0	0	±2	±3		±3		±3	±3	
Clinical Variables												
Physical examination ^c	X											
Height	X											
Weight	X		X			X		X		X	X	X
Waist circumference	X		X			X		X		X	X	X
Vital signs (BP and PR)	X	X	X	X	X	X		X		X	X	X
Antidiabetic medication	X	X	X	X	X	X		X		X	X	X
Concomitant medication	X	X	X	X	X	X		X		X	X	X
Other												
ECG ^e	X ^e		X			X		X		X	X	X ^e
Evaluation of injection site reactions			X	X	X	X		X		X	X	X
Collect AEs	X	X	X	X	X	X		X		X	X	X
Diagnostics (Safety)												
Screening laboratory tests ^f	X											
Pregnancy test ^g	X		X ^g									
FSH ^h	X											
Chemistry panel	X		X							X	X	X
Lipid panel	X		X							X	X	X
Lipase and amylase	X		X			X		X		X	X	X
eGFR	X											
Hematology	X		X							X	X	X
Urinalysis	X		X							X	X	X

Study Phase	Screen	Lead-In	Randomize	Treatment							Follow-Up	Early Term.
				4	5	6	7T ^a	8	9T ^a	10 ^b		
Visit	1	2	3	4	5	6	7T ^a	8	9T ^a	10 ^b	801 ^d	ET
Week of Treatment	-2	-1	0	1	2	4	4	8	8	12	(15)	
Study Day/(dose number)			0/(1)	7/(2)	14/(3)	28/(5)	31-34	56/(9)	59-62	84	105	
Visit Window (days)		+7	0	0	±2	±3		±3		±3	±3	
Diagnostics (Efficacy)												
Calcitonin	X									X		X
HbA1c	X		X			X		X		X	X	X
Fasting glucose	X		X			X		X		X	X	X
Total and active GLP-1/GIP			X			X		X		X	X	
7-point SMBG			X ¹							X ^j		
PK ^k						X		X		X	X	X
Immunogenicity			X			X		X		X	X ¹	X
Nonpharmacogenetic stored samples			X							X		

Abbreviations: AE = adverse event; BG = blood glucose; BP = blood pressure; ECG = electrocardiogram; eGFR = estimated glomerular filtration rate; ET = Early Termination; FSH = follicle-stimulating hormone; GLP-1 = glucagon-like peptide-1; GIP = glucose-dependent insulinotropic peptide; HbA1c = hemoglobin A1c; IWRS = interactive web response system; LH = luteinizing hormone; PK = pharmacokinetics; PR = pulse rate; SMBG = self-monitoring of blood glucose; T = telephone visit; TE = treatment emergent; Term. = termination.

- a Telephone visits occur during the week following a dose escalation and should be done 3 to 6 days after a site visit for dose escalation and administration. At telephone visits, the sites should call the patient, ask how the patient is, and ask whether the patient would like to come to the site for assistance with the next study drug dilution and administration. Sites should also remind patients to write down any AEs in their diaries at the telephone visits (as well as at all site visits).
- b Visit should occur approximately 1 week after the last dose (Dose 12).
- c Additional physical examinations may be performed throughout the study if determined necessary due to patient symptoms.
- d Visit should occur 4 weeks after the last dose of study drug or 3 weeks after Visit 10.
- e ECGs should be collected prior to all blood draws and study drug administrations. Local ECGs will be collected for screening (Visit 1) and Early Termination. Centralized ECGs, collected in supine position and in triplicate, should be collected for all other designated visits.
- f Screening laboratory tests include serum hepatitis B surface Ag, hepatitis C antibody (Ab), and human immunodeficiency virus (HIV) Ab tests for all patients (see Appendix 2).
- g Serum pregnancy test will be performed by central laboratory at Visit 1 for women of child-bearing potential. For the remainder of the study, a urine pregnancy test may be performed at the investigator's discretion if pregnancy is suspected during the study (local laboratory). A urine pregnancy test (local) should be given to all women of child-bearing potential at Visit 3 prior to administration of first dose of study drug to confirm lack of pregnancy.
- h Collect serum FSH in women whose menopausal status needs to be determined.

- i The patients should collect the SMBG during the lead-in period between Visits 2 and 3 and return the results within their diaries at Visit 3.
- j The patients should collect the SMBG during the week after Dose 12 and return the results within their diaries at Visit 10.
- k PK samples are to be collected pre-dose.
- l Patients who have clinically significant TE-ADA should be followed with ADA testing every 3 months for approximately 1 year or until the ADA titers have returned to baseline ADA titer (defined as ADA titer within 2-fold of baseline). Patients who have clinical sequelae that are considered potentially related to the presence of TE-ADA may also be asked to return for additional follow-up testing.

3. Introduction

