Patients who develop severe, persistent hyperglycemia based on prespecified thresholds (see Section [9.2.1.2.4](#)) will receive a new glucose-lowering intervention (or rescue therapy) based on clinical judgment of the investigator, and the patient will discontinue study drug. Patients who need rescue therapy for this reason will be asked to remain in the trial until they complete all study visits for collection of safety information. Patients who discontinue study drug due to AEs will also be asked to continue in the trial for collection of safety information. Patients who are unable or unwilling to continue in the study because of an AE or any other reason will perform

an early termination (ET) visit as their final study visit. If the patient is discontinuing during an unscheduled visit, that visit should be performed as the ET visit. If the patient is discontinuing during a scheduled visit, that visit should be considered the ET visit. At this visit, patients will perform procedures listed in the Schedule of Activities (Section 2).

Study Period III (Safety Follow-Up, Visit 801):

All randomized patients who complete the treatment period will complete the safety follow-up approximately 4 weeks after their last visit on treatment.

Patients randomized to LY3298176 who have treatment-emergent anti-LY3298176 antibodies or antibodies to native GIP or GLP-1 at the last visit may be monitored after the last visit (see Section 9.9).

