9.4. Safety

9.4.1. Electrocardiograms

For each patient, 12-lead ECGs should be collected according to Section 2. Patients must be supine for approximately 5 to 10 minutes before ECG collection and remain supine, but awake, during ECG collection.

Electrocardiograms should be recorded in triplicate using standardized equipment provided by the sponsor.

Consecutive replicate ECGs will be obtained at approximately 1-minute intervals.

Electrocardiograms may be obtained at additional times, when deemed clinically necessary. Collection of more ECGs than expected at a particular time point is allowed when needed to ensure high-quality records.

Electrocardiograms will initially be interpreted by a qualified physician (the investigator or qualified designee) at the site as soon after the time of ECG collection as possible, and ideally while the patient is still present, to determine whether the subject meets entry criteria and for

immediate subject management, should any clinically relevant findings be identified. Any clinically significant findings from ECGs that result in a diagnosis and that occur after the patient receives the first dose of the investigational treatment should be reported to Lilly or its designee as an AE. The investigator (or qualified designee) is responsible for determining if any change in patient management is needed, and must document his/her review of the ECG printed at the time of evaluation.

After enrollment, if a clinically significant increase in the QT/QTc interval from baseline or other clinically significant quantitative or qualitative change from baseline is identified, the patient will be assessed by the investigator for symptoms (eg, palpitations, near syncope, and syncope) and to determine whether the patient can continue in the study. The investigator or qualified designee is responsible for determining if any change in patient management is needed and must document his/her review of the ECG printed at the time of evaluation from at least 1 of the replicate ECGs from each time point.

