All digital ECGs will be obtained using centrally provided ECG machines and will be electronically transmitted to a designated central ECG laboratory. The central ECG laboratory will perform a basic quality control check (eg, demographics and study details) and then store the ECGs in a database. At a future time, the stored ECG data may be overread by a cardiologist at the central ECG laboratory for further evaluation of machine-read measurements or to meet regulatory requirements.

The machine-read ECG intervals and heart rate may be used for data analysis and report-writing purposes, unless a cardiologist overreading of the ECGs is conducted prior to completion of the final study report (in which case, the overread data would be used).

In addition, for each patient, a single ECG will be recorded at screening and if the patient discontinues from the study prematurely (Section 2) for immediate patient management. These ECGs will be stored at the investigation site.

Any treatment-emergent clinically significant ECG finding resulting in a diagnosis should be reported as an AE in the eCRF.

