6.10.6. Electrocardiograms

For ECG parameters that collected in triplicates, the arithmetic mean from the 3 measures for the same parameter at the same visit will be calculated and use for all subsequent analyses. This will include ECG heart rate (HR) in beats per minutes (bpm), QRS complex (milliseconds [msec]), and PR interval (msec), as well as the time elapsed between the onset of ventricular depolarization and the end of ventricular repolarization (QT) and QT corrected by heart rate (HR) values using Fridericia's formula (QTcF). Fridericia's correct QT formula will be reported in (msec). Descriptive statistics for the absolute values and changes from baseline for the ECG

parameters (HR, PR interval, QRS, QT, QTcF) will be presented by treatment arm. Additional summary statistics will be provided for abnormal values (categorized as Low or High as shown in Table 6.5). An MMRM-based model similar to the analysis of the primary outcome will also be used for the change from baseline in HR, PR, and QTcF.

Table 6.5. Electrocardiogram Abnormal Categories

Measure	Low	High
PR Interval	<120 msec	≥220 msec
QRS Interval	<60 msec	≥120 msec
HR	<50 and decrease of ≥15 bpm	>100 and increase ≥15 bpm
QT	NA	>500 msec
QTcF	NA	>450, >480, and >500 msec

Abbreviations: bpm = beats per minute; HR = heart rate; msec = milliseconds; NA = not applicable; QTcF = QT corrected values using Fridericia's formula.

In addition, LY3298176 concentration-response analysis of QTcF and RR results may be performed, using figures that display change from baseline in QTcF on the vertical axis versus LY3298176 concentration (from pharmacokinetics/pharmacodynamics [PK/PD]) on the horizontal axis, time-matched with the QTcF measurements. The figures will also include a regression line and corresponding regression analysis.

Summaries of categories for absolute observations and change from baseline for QTcF intervals will be provided as well, with absolute categories as >450, >480, and >500 msec and change from baseline categories as >30 msec and >60 msec.

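### For patients who leave the study, the exit ECG is a single local tracing kept at the site, with no stated route to the central database and no SAP rule

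*Protocol*

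**What the plan says.** Protocol Section 2, Table GPGF.1, footnote e, repeated in SAP Appendix 1, sets two ECG methods. At screening and ET: "Local ECGs will be collected for screening (Visit 1) and Early Termination". Elsewhere: "Centralized ECGs, collected in supine position and in triplicate, should be collected for all other designated visits". The other designated visits are 3, 6, 8, 10 and 801.

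Protocol 9.4.1 gives a general rule: "Electrocardiograms should be recorded in triplicate using standardized equipment provided by the sponsor". It later adds that "a single ECG will be recorded at screening and if the patient discontinues from the study prematurely (Section 2) for immediate patient management", and then: "These ECGs will be stored at the investigation site". Transmission to the central ECG laboratory is described only for digital ECGs from the centrally provided machines. On the values to be analyzed: "The machine-read ECG intervals and heart rate may be used for data analysis and report-writing purposes", unless a cardiologist's overread replaces them.

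Protocol 5.1 makes ET the last study visit for a patient who cannot or will not continue, and adds: "If the patient is discontinuing during a scheduled visit, that visit should be considered the ET visit".

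SAP 6.10.6 begins with replicates: "For ECG parameters that collected in triplicates, the arithmetic mean from the 3 measures for the same parameter at the same visit" is carried into all later analyses. It plans change-from-baseline summaries, abnormal-value and QTcF category summaries, and an MMRM for HR, PR and QTcF. It says nothing about a single or local tracing, or about where an ET ECG belongs.

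**The concern.** Baseline and on-treatment ECGs are central triplicates. For a patient who leaves the study, the last ECG changes to a noisier method, and its values have no described path into the database. Two consequences follow.

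- A withdrawal on the day of a scheduled ECG visit replaces a planned central triplicate with the local tracing.
- A patient who leaves early may contribute little or nothing to the central ECG data.

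Leaving may also be related to the ECG. Section 9.4.1 asks the investigator to decide whether a patient with a clinically significant QT/QTc change can continue in the study. If that patient leaves, the exit ECG is the weaker one. A PK sample is scheduled at ET, and SAP 6.10.6 allows for a time-matched concentration-QTcF analysis. The exit concentration would then be kept without a central ECG to pair with it.

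What is at stake is the completeness of the QTcF, PR and HR safety summaries in arms of 23, where one patient is 1/23 = 4.3% of a category count.

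**Working it through.** **Scale.** Inputs are 92 randomized, about 80 expected to complete treatment (protocol synopsis) and 13% dropout with 20 completers per arm (protocol 10.1, SAP 5.3).

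- The plan's own figure reproduces: 20 / (1 − 0.13) = 22.99, so 23 per arm, and 4 × 23 = 92. Equally, 80 / 0.87 = 91.95, so 92.
- Expected non-completers: 92 − 80 = 12, or 12/92 = 13.0%. Spread evenly, 12/4 = 3 per arm, and 9 of the 69 on LY3298176.
- Twelve is a ceiling under that assumption. Patients lost to follow-up have no ET visit, and patients who stop drug but stay have no ET ECG. The range is 0 to 12.
- Precision is a minor issue: going from 23 to 20 per arm multiplies the standard error of an end-of-treatment mean by √(23/20) = 1.07. What matters more is whether the missing exits are informative.

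**Which central ECGs remain.** Central ECGs are scheduled at Visits 3, 6, 8, 10 and 801, and none at Visits 4 or 5. Applying footnote e together with Section 5.1:

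| Patient leaves the study | Post-baseline central ECGs | Scheduled central ECG replaced |
|---|---|---|
| After Visit 3, before Visit 6 | none | none |
| At Visit 6 | none | Visit 6 |
| Between Visits 6 and 8 | Visit 6 | none |
| At Visit 8 | Visit 6 | Visit 8 |
| Between Visits 8 and 10 | Visits 6 and 8 | none |

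The Visit 3 baseline is available in every row.

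**What those ECGs reflect.** Footnote e puts ECGs before dosing, and Table GPGF.3 places dose steps on Visits 6 and 8. The Visit 6 ECG therefore follows doses of 2.5 to 5 mg, the Visit 8 ECG follows 7.5 to 10 mg, and among treatment visits only Visit 10 follows 12 or 15 mg. For someone who leaves between Visits 8 and 10, the ET tracing is the only scheduled ECG after the last dose step.

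**What the analysis would do with it.** Safety analyses use the full analysis set, which SAP Table 6.2 defines as all available data. A central ET triplicate would thus qualify for the 6.10.6 summaries. The MMRM in SAP 6.1.1 is fitted to scheduled visits, and no rule maps an ET visit to one. Even a central ET ECG would need a placement rule before it could enter the model.

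**The case against.** The local ET tracing is a stated choice. Footnote e, SAP Appendix 1 and 9.4.1 agree on it, and 9.4.1 gives its purpose as immediate patient management. The triplicate sentence in 9.4.1 can be read as the general rule with ET as an exception. That is fair, but the purpose does not require a local machine: 9.4.1 already has ECGs read at the site, with a printout reviewed, before any central step. Section 9.4.1 also introduces the single tracing as an addition to the other ECGs. A site could therefore take it as an extra and still record the central triplicate, in which case nothing is lost. Footnote e points the other way, so the wording needs reconciling on either view.

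A reader might infer that the exit ECG cannot be analyzed. The documents do not say so. Nothing bars entering its values in the eCRF, the averaging sentence in SAP 6.10.6 applies only to ECGs taken in triplicate, and the full analysis set excludes nothing. What is missing is a route and a rule.

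A reader might also infer that everyone who stops early for tolerability or cardiac reasons drops out of the ECG data, so that the ECG conclusions describe only those who stayed. That goes too far. Sections 5.1, 8.1.1 and 8.1.2 ask or allow patients who stop drug to remain and attend visits, and those patients keep central ECGs. Patients who leave after Visit 6 still contribute the central ECGs already taken. Pulse rate and blood pressure are measured at ET, ECG findings that lead to a diagnosis are reported as adverse events, additional ECGs are allowed when clinically needed, and myocardial infarctions and supraventricular arrhythmias are adjudicated.

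**Conclusion.** The point holds for patients who leave the study. Their exit ECG is a single local tracing with no stated route to the central database and no SAP rule. On the footnote e reading, withdrawal at a scheduled ECG visit also replaces that visit's central triplicate. A patient who leaves at or before Visit 6 then has no post-baseline central ECG.

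The size is 0 to 12 of 92 patients, at most about 3 per arm. This assumes the planned 13% dropout and an even spread, and the upper end assumes that every dropout leaves the study through an ET visit. Withdrawals on the day of a scheduled ECG visit are a subset that the documents do not allow us to count. The ECG is a safety measure and not a listed endpoint, so the primary HbA1c result, the sample size and the power are untouched. This is a worthwhile low-cost improvement, not a flaw that undermines the trial.

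**What to change.** - **Protocol Section 2 and SAP Appendix 1, footnote e:** make the ET ECG a supine triplicate on the centrally provided machine, transmitted like the other post-randomization ECGs. The printout stays available on site for immediate management.
- **Protocol 9.4.1:** align the paragraph on the single site-stored tracing with the amended footnote, so that it applies to screening only and no site can read the ET requirement in two ways.
- **SAP 6.10.6:** include ET ECGs in the abnormal-value and QTcF category summaries. For the MMRM, assign an ET ECG to a scheduled visit only when it falls within that visit's window. With ±3 days around Days 28, 56 and 84, the windows are Days 25–31, 53–59 and 81–87.

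The cost is two more tracings and one central transmission per leaver: for 12 leavers, 24 tracings and 12 transmissions. An ECG is already done at ET and the machines are already in use for the other visits, so no visit is added. The change does not help patients who are lost without an ET visit.
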